2.3 RISK/BENEFIT ASSESSMENT

See the Data & Safety Monitoring Plan

3 OBJECTIVES AND ENDPOINTS

OBJECTIVES	ENDPOINTS	JUSTIFICATION FOR ENDPOINTS
Primary		
Aim 1. Examine the feasibility of the MC Approach for people with PD within an RCT.	Recruitment, Retention, Intervention duration	Understanding and optimizing the procedures of an RCT of a complex behavioral intervention is necessary before evaluating outcomes ⁵⁸⁻⁶⁰ . We will track recruitment, retention, and intervention duration to ensure we can maintain a productive flow of participants and complete treatment in a reasonable timeframe. We will record reasons for attrition and examine characteristics of those who drop out to inform retention-enhancing strategies for the definitive RCT.
Aim 2. Demonstrate adequate treatment fidelity to the MC Approach.	Therapist Adherence & Proficiency; Participant Acceptance,	Appropriate delivery (Adherence & Proficiency) is the foundation of treatment fidelity ^{55,61} . To achieve the desired outcomes of any behavioral intervention, participants also must “buy into” its principles and practices (Acceptance), actively

OBJECTIVES	ENDPOINTS	JUSTIFICATION FOR ENDPOINTS
	Receipt, & Enactment	engage with the content during treatment (Receipt), and apply the learned skills in relevant real-life settings (Enactment) ^{54,55} .
Aim 3. Obtain preliminary estimates of effect on patient-reported functional cognition.	Bangor Goal Setting Interview	Functional cognition—how cognitive abilities enable/disable function in daily activities—is the primary target of cognitive rehabilitation and is now recognized as an important outcome in PD cognitive research ^{62,63} . Patient-reported outcomes are increasingly used to measure this type of construct since it is not directly observable in research or clinical settings and because the patient's experience is a key determinant of treatment value ⁶⁴ . In best practice cognitive rehabilitation, the therapist and client collaborate to identify problems with functional cognition and set related treatment goals ^{15,28} , and progress on those problems/goals determines treatment success. To be consistent with real-world practice and, therefore, to facilitate future clinical implementation, we will use this same process to determine treatment effect.
Secondary		
To obtain preliminary estimates of effect on other measures of functional cognition.	Weekly Calendar Planning Task, Self-regulation Skills Inventory, NeuroQOL Cognitive Function, PD-Cognitive Functional Rating Scale	
To obtain preliminary estimates of effect on self-efficacy.	Cognitive Self-efficacy Scale, General Self-efficacy Scale	
Tertiary/Exploratory		
To obtain preliminary estimates of effect on participation.	NeuroQOL Ability to Participate in Social Roles and Activities	

The following criteria will be used to declare failure:

Aim 1: Feasibility

- ≤ 60% retention in the study intervention

- $\leq 75\%$ retention in the study (80-85% is typically considered good in behavioral trials; e.g., Abshire et al., 2017; Coday et al., 2005)
- Note: Participants excluded post-Randomization count as failures in the above retention endpoints.

Aim 2: Fidelity

- Therapist adherence to protocol: Average $\leq 75\%$
- Therapist competence in administration: Average < 2
- Participant satisfaction: Average Client Satisfaction Questionnaire score ≤ 16
- Participant engagement: Average Rehabilitation Participation Scale score ≤ 3

Aim 3: Effect

- Average Bangor Goal Setting Interview Goal Attainment change of ≤ 1 with lower 95% CB below 0.

4 STUDY DESIGN

4.1 OVERALL DESIGN

We will conduct a single-site, single-blind pilot RCT. Participants will complete pre-treatment assessment and then will be randomized to treatment arm (stratified by sex and MoCA score [25/26]⁶⁵). Both arms will consist of 10 individualized treatment sessions within a 12-week period. In-person post-treatment assessment will be 1 week after intervention completion, and questionnaire follow-up will be 3 months after.

See also Sections 1.1, 1.2, 2.1, 2.2, 3

4.2 SCIENTIFIC RATIONALE FOR STUDY DESIGN

This project will build on our prior work to assess and optimize the feasibility of the MC Approach for people with PD in a pilot RCT and to generate data to power a definitive RCT. This Stage I study is part of a rigorous developmental process designed to optimize the intervention for future efficacy or effectiveness trials and eventual translation into clinical practice. It will provide us with feasibility data, fidelity enhancements, clinical trials infrastructure, experience training and monitoring therapists, and an estimate of treatment effect—all essential elements for efficiency, rigor, reproducibility, and payoff in future clinical trials as well as for implementation and sustainability in real-world clinical practice.

See also Sections 1.1, 1.2, 2.1, 2.2, 3

4.3 JUSTIFICATION FOR INTERVENTION

Both treatments consist of 10 ~1-1.5 hour sessions over 12 weeks delivered in an individual, face-to-face format in participants' homes and/or communities by trained licensed occupational therapists (OTs). Both are realistic and reimbursable services within our current healthcare system.

See also Sections 2.1, 2.2, 3, 6

4.4 END-OF-STUDY DEFINITION

A participant is considered to have completed the intervention if he or she has completed the baseline assessment and 10 intervention sessions.

Completion of the study is defined as completion of the 3-month follow-up assessment.

5 STUDY POPULATION

5.1 INCLUSION CRITERIA

Males and females over age 40 who meet criteria for typical idiopathic PD⁶⁶, are stage I-III⁶⁷, have subjective cognitive decline (SCD)⁶⁸ (as defined by a positive answer to either question: Do you feel like your thinking skills or memory are becoming worse? Do you have problems with your thinking skills or memory?), and can list ≥ 1 daily cognitive challenge they wish to address. Medications should be stable for 4 weeks prior with no changes planned during the study.

Rationale for cognitive criteria for entry: We will include people with SCD regardless of whether they meet diagnostic criteria for PD-MCI. There is no gold standard assessment of SCD, so we are using a common method of ascertainment based on research criteria for SCD^{68,69}. People with SCD are an important target for cognitive treatment because SCD may be a more sensitive measure of cognitive decline than cognitive tests in high functioning or at-risk individuals⁶⁸ and, in the absence of objective deficits, SCD predicts future development of PD-MCI^{70,71}. Because the MC approach is client-centered, we hypothesize that it can meet the needs of people with SCD with or without objective cognitive deficits. Our preliminary study⁵³ supports this notion, as both kinds of participants (using MoCA cutoff 25/26)⁶⁵ reported improved functional cognition from the MC approach. To begin to explore this issue more thoroughly in the current study, we will recruit people with SCD and then use neuropsychological testing to characterize cognitive status (\pm PD-MCI) and assess it as a potential effect modifier. This study is not powered to detect significant effects of this factor, but our findings will guide sampling, inform hypotheses, and provide preliminary data for future trials.

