6.3 MEASURES TO MINIMIZE BIAS: RANDOMIZATION AND BLINDING

Participants will be randomized to treatment arm (MC, Control)* stratified by sex and MoCA score [25/26]⁶⁵. The study statistician created a randomization process that is implemented through REDCap by an independent person ([name]). Immediately after a participant completes Pre assessment, the tester informs [name], via email, of their study ID, sex, and MoCA score (stratification variables). Within 2 days of being informed, [name] will use the REDCap randomizer to assign treatment group and will inform the corresponding therapists, via email, that a participant has been assigned to their group. Only [name] and the statistician can view the randomizer and its results. To maintain PI blinding during therapist supervision, the participants or treatment sessions under discussion will not be identified by study ID.

Personnel collecting Pre, Post and Follow-up data, which includes the study coordinator, will remain blind to treatment arm throughout the entirety of the study. They will not know which therapists are administering which intervention. Inadvertent unblinding of testers will be documented (yes/no, notes). Most of the outcomes, including the primary efficacy outcome (BGSI, Aim 3), are collected via computer, so inadvertent unblinding should not bias the data.

Personnel responsible for rating the audio files for fidelity (Aim 2) will be blind to study purpose. Due to the nature of their work, they will likely come to understand that there are two general intervention approaches being delivered and which therapists are delivering which approach; however, having no knowledge of the study aims and hypotheses and clear criteria for rating should reduce any associated biases in their ratings.

Participants will be aware that they have been randomly assigned to one of two interventions, but they will be given no information on what the other intervention entails, nor will they be informed which is the hypothesized “active” (MC) or Control intervention. In the Follow-up assessment, participants will be asked if they think they received the active or control intervention (yes/no/I don’t know with an option to provide an open-ended response describing why).

*Randomization ratios over the course of the study due to therapist availability:

- November 2019-December 2020 = 2:1, MC:Control
- January 2021- ~2021 = 1:2, MC:Control
- ~July 2021- = 1:1, MC:Control

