For the Aim 2 outcomes, we will calculate mean scores $\pm 95\%$ confidence bounds (CBs) and compare them to our stated thresholds. To assess treatment differentiation, we will compare Proficiency scores for the MC and Control sessions using *t*-tests. We can also categorize participants using cutoffs (e.g., homework: <50% = Poor, 50-79% = Fair, $\geq 80\%$ = Good) for descriptive purposes and compare the MC and Control groups’ scores on outcomes using appropriate non-parametric tests.

Aim 3: Obtain preliminary estimates of the MC approach's effect on patient-reported functional cognition.

- H3 (exploratory): MC participants will report greater improvement in functional cognition than Control participants immediately and 3 months after treatment.

We will compare treatment effects (Goal Attainment) using mixed model repeated measures ANOVA (2: group X 3: time point). We chose this model because we want to use statistical contrasts to compare pre-post and pre-follow up changes across group. We will evaluate the pattern of correlations within subjects and test various correlation structures as appropriate using Akaike's information criteria and the Schwarz Bayesian criteria. However, our purpose is not to demonstrate efficacy, but rather to obtain effect size data to inform sample size calculations for a definitive RCT. To this end, we will generate mean change between the time points with 95% CIs. We will compare these data to the suggested minimally clinically important difference (≥ 2 points improvement)⁸⁹ to help determine the appropriate sample size to test the hypothesis that, in addition to being superior to the Control treatment, MC produces a clinically significant effect⁹⁰. We will also create a sample size table for various effect size values due to uncertainty of pilot estimates⁹¹.

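### The Aim 3 model leaves out the factors that stratify randomization, and section 9.4 specifies no analysis for the exploratory effect-modifier assessment promised in section 5.1

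*Combined protocol and SAP*

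**What the plan says.** On randomization, section 6.3 has participants "stratified by sex and MoCA score [25/26"], and section 4.1 says the same.

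On the Aim 3 analysis, section 9.4 states: "We will compare treatment effects (Goal Attainment) using mixed model repeated measures ANOVA (2: group X 3: time point"). It adds contrasts of pre-post and pre-follow-up change between groups, mean changes with 95% CIs, and a choice of correlation structure. No other term is named.

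On cognitive status, section 5.1 states: "We will include people with SCD regardless of whether they meet diagnostic criteria for PD-MCI". It goes on to say that the trial will "use neuropsychological testing to characterize cognitive status" and "assess it as a potential effect modifier". It is open about the limits: "This study is not powered to detect significant effects of this factor". It also gives the work a purpose: "our findings will guide sampling, inform hypotheses, and provide preliminary data for future trials".

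Nothing in section 9 mentions sex, MoCA, PD-MCI, a subgroup or a moderator. Section 8.1 says some of the additional data may serve as covariates but names none.

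**The concern.** There are two gaps, both in the Aim 3 paragraph of section 9.4.

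First, the analysis does not follow the design. Stratifying balances the arms on sex and MoCA stratum. A model without those factors leaves whatever variation they explain in the residual, so the reported interval does not take credit for that balance. Aim 3 exists to supply effect-size estimates with intervals for planning the definitive RCT, so unnecessary width is a cost to its purpose.

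Second, a promised output has no analysis behind it. A group by time model returns one average effect over participants with and without objective deficits. A covariate main effect would not repair this, because effect modification needs an interaction or separate subgroup estimates. Leaving the analysis open also leaves the choice of definition (PD-MCI or MoCA cut-off) and of contrast until after the data are seen.

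**Working it through.** **Inputs.** From section 9.2: 30 per group, SD of Goal Attainment change 0.97, detectable difference 0.85, two-sided alpha 0.05, power 90%, and 15% attrition (used there for the feasibility and fidelity aims). The share of participants with PD-MCI or in the lower MoCA stratum is not given, so I vary it. I assume SD 0.97 in every cell, equal arms within each subgroup, and the same SD for the follow-up contrast.

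**The plan's own figure.** Detectable difference = 0.97 × (1.960 + 1.282) × √(2/30) = 0.81 by the normal approximation and 0.83 by noncentral t. Conversely, 0.85 needs 28 (normal) or 29 (t) per group. The stated 0.85 with 30 per group is therefore reproduced and slightly conservative. It allows for no attrition: at 25.5 per group the figure is 0.88 (normal) or 0.90 (t). It concerns the group contrast only.

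**Cost of omitting the stratification factors.** Unadjusted SE / adjusted SE = 1/√(1 − R²), where R² is the share of variance in change that the factors explain. No value is in the documents.
- R² = 0: ratio 1.00, no loss.
- R² = 0.05: 1/√0.95 = 1.03.
- R² = 0.10: 1/√0.90 = 1.05, about 5% too wide.

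The time interactions matter. A stratum main effect shifts all three time points equally and does not sharpen a contrast of change.

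**MC–Control difference within one subgroup.** Half-width = 1.96 × √(2 × 0.97² / n), with n per arm in that subgroup (normal approximation).

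| Split | n per arm, no attrition | Half-width | n per arm, 15% attrition | Half-width |
|---|---|---|---|---|
| Even | 15 | 0.69 | 12.75 | 0.75 |
| One third, smaller subgroup | 10 | 0.85 | 8.5 | 0.92 |

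The one-third row borrows the rough proportion that section 2.2 gives for mild deficits in the earliest stages of PD. That figure is not specific to a sample selected for subjective decline.

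**Difference between subgroups (the modifier contrast).** Variance = 2 × 0.97² × [1/(mf) + 1/(m(1 − f))], with m per arm and f the share with the modifier. Half-width uses t on N − 4 df.

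| f | SE, N = 60 | Half-width | SE, N = 51 | Half-width |
|---|---|---|---|---|
| 50% | 0.50 | 1.00 | 0.54 | 1.09 |
| One third | 0.53 | 1.06 | 0.58 | 1.16 |
| 20% | 0.63 | 1.25 | 0.68 | 1.37 |

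The overall group contrast has SE 0.97 × √(2/30) = 0.25, so the modifier contrast has twice that SE even at the most favourable split. Power to detect a 0.85-point interaction runs from about 38% (N = 60, even split) down to 23% (N = 51, 20% share). About 219 participants would be needed for 90% power at an even split: 16 × (0.97 × 3.24 / 0.85)² ≈ 219. This agrees with section 5.1's own statement that the study is not powered for the factor.

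**The case against.** The strongest reply is that this is a pilot which disclaims efficacy testing. Effect modification is not a listed objective, endpoint or hypothesis. Section 9.4 covers only the numbered aims and gives no analysis for the secondary outcomes either. Section 6.5 likewise places an exploratory analysis outside section 9. On this view the modifier work is simply unspecified, and section 5.1 already says it is exploratory and unpowered. Much of that stands: the second gap is a missing specification, not missing power and not an analysis that the plan rules out. It does not answer the first gap, because the Aim 3 model is specified and omits the factors that the design uses.

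A reader might also infer more than the documents support:
- *That the trial cannot address effect modification.* This is true of section 9.4 as written but not of the data. MoCA, sex and the NIH Toolbox battery are all collected at the pre-treatment visit.
- *That broad entry exists only to study modification.* Section 5.1 first presents people with subjective decline as a treatment target in their own right.
- *That the MoCA stratum should replace PD-MCI because the arms are balanced on it.* Section 5.1 chooses neuropsychological testing as a more thorough step than the MoCA cut-off used in the preliminary study, and estimating modification does not require stratifying on the modifier.
- *That these half-widths are adequate because they are small against 2 points.* In section 9.4 that figure is a benchmark for improvement, not for differences between arms or subgroups. The plan's between-arm yardstick is 0.85, and every between-subgroup half-width above exceeds it.

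**Conclusion.** The point holds in two parts. The Aim 3 model ignores sex and MoCA stratum, so its intervals are wider than necessary if those factors predict change. The loss is about 5% at an assumed R² of 0.10 and nil if they predict nothing. The group comparison remains valid; the issue is precision.

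Separately, section 5.1 promises an exploratory modifier assessment, and section 9.4 contains nothing that delivers it. Once specified, the between-subgroup estimate would have a 95% half-width of about 1.0 to 1.4 points, assuming SD 0.97 throughout, a modifier share of 20–50% and up to 15% attrition. That can inform the sampling of the definitive RCT. It cannot decide whether that trial should require objective impairment.

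**What to change.** In section 9.4, under Aim 3:
1. Add MoCA stratum (25/26) and sex to the model, each with its interaction with time point.
2. Add an exploratory group by time by cognitive-status term, with its lower-order terms. Keep PD-MCI by neuropsychological testing as the stated modifier, and report the MoCA stratum alongside it in a parallel analysis.
3. State the rule that classifies PD-MCI from the baseline tests, since the documents give none, and fix it before outcome data are examined.
4. Report pre-post and pre-follow-up MC–Control differences with 95% CIs in each subgroup, labelled as estimation only.

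The cost is SAP wording and one table. No new data are needed and nothing changes for participants. The downside is a few degrees of freedom and wide exploratory intervals that must be labelled as such.

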5.2 EXCLUSION CRITERIA

Dementia according to MDS criteria⁷² or MoCA score < 21 ⁶⁵, other neurological disorders (e.g., stroke), brain surgery (e.g., STN DBS), history of psychotic disorder or any significant current psychiatric disorder, or any condition that would interfere with participation (e.g. non-English speaking).

5.3 LIFESTYLE CONSIDERATIONS

During this study, participants are asked to:

- Refrain from engaging in OT or other cognitive interventions.

5.4 SCREEN FAILURES

Screen failures are defined as participants who do not meet eligibility criteria upon record or phone screen and are not enrolled in the study.

Individuals who are ineligible to participate in the study because of not meeting criteria that could change over time may be rescreened. Examples include the development of SCD or emergence of functional cognitive goals.

5.5 STRATEGIES FOR RECRUITMENT AND RETENTION

See Recruitment & Retention and Inclusion of Women & Minorities.

6 STUDY INTERVENTION(S) OR EXPERIMENTAL MANIPULATION(S)

6.1 STUDY INTERVENTION(S) OR EXPERIMENTAL MANIPULATION(S) ADMINISTRATION

6.1.1 STUDY INTERVENTION OR EXPERIMENTAL MANIPULATION DESCRIPTION

MultiContext Approach (MC):

This treatment focuses on improving functional performance by enhancing the generation and use of strategies—which can be internal (e.g., self-talk, planning) or external (e.g., checklist, alarm)—to circumvent cognitive processing limitations caused by PD. It uses a standardized approach across and within sessions for all clients while being tailored to each client’s cognitive problems and goals. The first two sessions are OT evaluation sessions designed to (1) provide the OT with a comprehensive understanding of the client’s functional cognition, occupational performance and participation, (2) begin building the client’s awareness of cognitive strengths and limitations and how they may relate to daily function, and (3) inform individualized goal setting and treatment planning. They involve an explanation of MC’s purpose and process, OT functional cognitive “diagnostic” assessments (the WCPA, SRSI, structured treatment activity), review of pre-treatment assessments, collaborative goal setting (BGSI), and assignment and review of the cognitive log homework (record and reflect on daily cognitive lapses). All subsequent treatment sessions consist of a review of prior sessions and learning, homework review, treatment activities, homework provision, and session recap. Each session’s treatment activities are selected collaboratively based on the client’s goals and preferences and the OT’s assessment of the client’s cognitive and functional status. They involve the performance of simulated functional activities with OT mediation and a metacognitive framework to help the client anticipate performance problems, generate and use strategies to support performance, evaluate and modify performance and strategy use, and transfer these principles to other activities. The OT’s expertise in functional cognition, task and performance analysis, and task manipulation and grading guides this process. Treatment activities also involve in-depth discussion of these issues, including making explicit connections between the simulated functional activities, strategies, and the client’s real-life experiences, to promote generalization of learning^{40,41}. Homework consists of action plans for using the strategies generated and practiced during the treatment session in specific everyday life situations. Clients record instances of strategy use (or

missed opportunities) along with their evaluation of strategy effectiveness and potential modifications on a structured worksheet, which is reviewed collaboratively in the next session. In this way, homework not only supports real-life strategy application and practice, but it also reinforces self-monitoring, self-evaluation, problem solving, strategy self-generation, and strategy optimization. Treatment progresses through three general phases (1: Understand and define problems and goals, 2: Generate, execute, and evaluate strategies, 3: Generalize and reinforce strategy use) and increases in difficulty, but progression is flexible depending on the client's goals and abilities.

Control:

This treatment parallels the cognitive process training used in PD to-date but with simulated functional tasks (vs. computer or paper & pencil tasks). It has the same basic protocol as MC, but it is therapist-directed, and the OT does not address strategies, metacognition, generalization, or use mediation or action plans. Therefore, this is a standard-of-care approach that includes all but the proposed critical elements of MC. The OT reviews pre-treatment cognitive test scores with the client but without discussion to build awareness. The OT selects treatment activities based on the client's cognitive profile and goals from a published set of activities designed for use in cognitive interventions⁷³. Graded task practice with OT feedback on performance accuracy is used to produce neurocognitive improvement (or possibly independent strategy development). The OT assigns practice of specific cognitively challenging everyday life activities for homework (but without action plans).

